### 6.6.3.2. Exposure to Lenalidomide

Starting on Cycle 1, the first dosing of the two combination partners (lenalidomide and dexamethasone) will be initiated.

Escalating doses of 15 mg or 25 mg of lenalidomide PO QD will be administered on Days 1-21 of each 28-day cycle for all cycles. De-escalating dose of 10 mg is permitted, depending on the dose levels being evaluated.

The summary of treatment exposure to lenalidomide will include the following information:

- Treatment duration (weeks);
- Total cumulative dose (mg);
- Overall dose intensity (mg/week);
- Overall relative dose intensity (%).

The treatment duration of lenalidomide (in weeks) during the study for a participant is defined as:

- Treatment duration (weeks) = (last dose date - first dose date + 1)/7

Planned treatment duration, intended treatment duration, planned dose and planned DI is needed to calculate DI and RDI. The planned treatment duration is defined as:

- Planned treatment duration (weeks) = (number of cycles started x 4) - (number of weeks in the last cycle after permanent treatment discontinuation or data cutoff for those on-treatment).
- Intended treatment duration (weeks) = (last zero/non-zero dose date – first dose date)/7 + 1
- Planned dose (mg/cycle) = Full dose (mg) × 21, Full dose=15, 25 or 10 depending on DL.

**Note:** For last cycle, subtract planned doses after a participant permanently discontinues treatment or data cutoff for those on-treatment.

The total planned dose is the sum of the total planned dose across all cycles.

The total cumulative dose (mg) of Lenalidomide is the sum of the actual dose levels that the participant received during the study (ie, total dose administered [mg]).

The overall planned DI is defined as:

- Overall Planned DI (mg/week) = Total planned dose (mg)/(planned treatment duration in weeks).

The overall DI and RDI of lenalidomide will be calculated for each participant during the study.

- Overall DI (mg/week) = Total cumulative dose (mg)/ Intended treatment duration (weeks);
- Overall RD (%) = [Total cumulative dose (mg) / Total planned dose (mg)] × 100;
- Overall RDI (%) = [Overall DI (mg/week) / Overall Planned DI (mg/week)] × 100.

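### Sub-study B SAP 6.6.3.2: lenalidomide relative dose intensity is not 100% when every planned dose is taken, because intended and planned duration cover different periods

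*SAP*

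**What the plan says.** Sub-study B SAP 6.6.3.2 gives the schedule: "lenalidomide PO QD will be administered on Days 1-21 of each 28-day cycle for all cycles". The definitions that matter are these.

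- Intended duration: the formula opens "Intended treatment duration (weeks) = (last zero/non-zero dose date" and in full reads "Intended treatment duration (weeks) = (last zero/non-zero dose date – first dose date)/7 + 1". The final 1 stands outside the division, so it is a week, not a day.
- Planned duration: four weeks per cycle started, less the "number of weeks in the last cycle after permanent treatment discontinuation or data cutoff for those on-treatment".
- Planned dose: "Planned dose (mg/cycle) = Full dose (mg) × 21, Full dose=15, 25 or 10 depending on DL", with a note on the final cycle: "For last cycle, subtract planned doses after a participant permanently discontinues treatment or data cutoff for those on-treatment".
- Dose intensity (DI): "Overall DI (mg/week) = Total cumulative dose (mg)/ Intended treatment duration (weeks"). Planned DI is total planned dose over planned duration, and overall RDI is DI as a percentage of planned DI.

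Overall DI and overall RDI are on the section's list of lenalidomide summaries. Overall relative dose (RD), the cumulative dose as a percentage of the planned dose, is defined in the section but is not on that list. Treatment duration, a separate quantity there, adds one day inside the division.

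**The concern.** A participant who takes every planned dose on time should have an RDI of 100%. Here the denominator for the dose taken always carries an extra week beyond the last dose date, while the planned side stops at discontinuation or cutoff. A participant who stops early without missing a dose is then reported as under-dosed. Discontinuation, which belongs in the duration and disposition summaries, is mixed into dose intensity.

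Dose levels are small: sub-study B SAP 5.1.1.1 plans 3 to 6 DLT-evaluable participants each, and 5.2 asks for analysis by dose level. As an illustration, two participants at 100% and one fully compliant participant reported at 62.5% give a mean of (100 + 100 + 62.5)/3 = 87.5%.

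**Working it through.** The plan states no RDI value, so there is no figure to reproduce. All inputs come from sub-study B SAP 6.6.3.2: 21 daily doses in a 28-day cycle, and the definitions above.

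**Reduction.** With full compliance the cumulative dose equals the planned dose, so the mg dose cancels:

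RDI = 100 × planned duration / intended duration.

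**Base reading.** Part-weeks are counted as days/7, rest days (Days 22 to 28) are not zero-dose records, and planned duration for a completed cycle runs to Day 28.

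*Stop on dosing Day d of Cycle 1.* Intended = (d − 1)/7 + 1 = (d + 6)/7 weeks. Planned = 4 − (28 − d)/7 = d/7 weeks. RDI = d/(d + 6).

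- Day 5: 5/11 = 45.5%
- Day 10: 10/16 = 62.5%
- Day 14: 14/20 = 70.0%

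*Stop on Day 10 of Cycle N.* RDI = (28(N − 1) + 10)/(28(N − 1) + 16).

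- Cycle 2: 38/44 = 86.4%
- Cycle 3: 66/72 = 91.7%
- Cycle 6: 150/156 = 96.2%
- Cycle 12: 318/324 = 98.1%

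*N completed cycles, last dose on Day 21.* Intended = (28(N − 1) + 20)/7 + 1 = (28N − 1)/7 weeks. Planned = 4N weeks. RDI = 28N/(28N − 1).

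- 1 cycle: 28/27 = 103.7%
- 2 cycles: 56/55 = 101.8%
- 12 cycles: 336/335 = 100.3%

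*DI itself, 25 mg, stop on Day 10 of Cycle 1.* The dose taken is 250 mg. Reported DI = 250/(16/7) = 109.4 mg/week. Planned DI = 250/(10/7) = 175 mg/week, which is also the rate actually taken.

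**Other readings the text allows.**

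- Whole weeks subtracted from planned duration, Day 10 stop: 18 days remain. Subtracting 2 weeks gives 2/(16/7) = 87.5%; subtracting 3 gives 1/(16/7) = 43.75%. Rounding down does return 100% on isolated days. For a Day 8 stop, 20 days remain, 2 weeks come off, planned is 2 weeks and intended is 7/7 + 1 = 2. This is a coincidence of rounding, not a property of the rule.
- Rest days recorded as zero doses, one completed cycle: intended = 27/7 + 1 = 34/7, so RDI = 28/34 = 82.4%.
- Discontinuation dated Day 21, one full course of 21 doses: planned = 3 weeks, intended = 27/7, so RDI = 21/27 = 77.8%.

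Overall RD is 100% in every case above.

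**The case against.** The best defence is that the added week roughly stands in for the rest week. For completed cycles under the base reading this is right: intended duration is one day short of planned, and RDI is at most 3.7 points high. The discrepancy after a mid-cycle stop is also a constant 6 days, so it matters little for participants with many cycles. Both points stand, and they limit the size of the problem. They do not cover the stop during dosing days in an early cycle, where no rest week is planned.

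Several stronger readings are tempting, but the documents do not support them.

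- *RDI is generally far from 100%, and always above it for completers.* The first fits early stops only. The second depends on how rest days and the discontinuation date are recorded, which the section does not settle.
- *RDI is the trial's measure of whether lenalidomide can be given with elranatamab.* The SAP does not say so. RDI is one listed descriptive summary. Escalation rests on DLTs and the BLRM with other clinical evidence (5.1.2.1), and the expansion part has no decision rule (5.1.2.2).
- *Sub-study A has the correct formula to copy.* Its nirogacestat version puts one day inside the division, but that drug is given continuously. Applied to lenalidomide it gives 100% for the Day 10 stop and 4/3 = 133.3% after one completed cycle.
- *The formula was carried over from the weekly drugs.* The same form does appear for elranatamab on weekly dosing and for dexamethasone, where one dose covers a week. How it came to be used here is not stated.

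**Conclusion.** The mismatch holds: intended and planned duration do not end on the same date, so full on-time compliance does not reliably give an RDI of 100%. The size is large for a stop early in Cycle 1, modest by Cycle 2 or 3, and small for completed cycles. The exact percentages rest on fractional part-weeks, unrecorded rest days and planned duration running to Day 28 of a completed cycle. The other readings move the values, and the text does not choose among them, which is itself a gap.

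Overall DI and overall RDI for lenalidomide are affected. No endpoint, decision rule or dosing decision is. Overall RD is unaffected, but because it is not on the summary list, the figure that would reveal the discrepancy may not be displayed. Severity: minor.

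**What to change.** End both durations on the same date. Define intended duration (weeks) = (end date − first dose date + 1)/7. The end date is the earliest of permanent lenalidomide discontinuation, data cutoff, and Day 28 of the last cycle started, whether or not rest days are recorded as zero doses. Count part-weeks as days/7 in planned duration.

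Check under full compliance:

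- One completed cycle: 28/7 = 4 weeks against 4, RDI 100%.
- Stop on Day 10 of Cycle 1: 10/7 against 10/7, RDI 100%.
- Cutoff on Day 24 of Cycle 1: 24/7 against 4 − 4/7 = 24/7, RDI 100%.

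A delay still counts: two completed cycles with one week lost between them give 8/9 = 88.9%.

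A simpler repair, one day inside the division plus seven days whenever Day 21 was reached and treatment continued, is not enough. For the Day 24 cutoff it gives 24/28 = 85.7%, worse than the present 24/27 = 88.9%. If rest days are zero-dose records it counts the week twice: 28/7 + 1 = 5 weeks, RDI 80.0%.

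Cost: one SAP formula and the exposure program.

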### 6.6.3.3. Exposure to Dexamethasone

Dexamethasone 20 mg will be administered three time in C0 (D1, D4, D8), and PO QW (D1, D8, D15, D22) during the first 2 cycles of the combination (C1 and C2).

The summary of treatment exposure for dexamethasone will include the following information:

- Treatment duration (weeks);
- Total cumulative dose (mg);
- Overall dose intensity (mg/week);
- Overall relative dose intensity (%).

The treatment duration of dexamethasone (in weeks) during the study for a participant is defined as:

- Treatment duration (weeks) = (last dose date – first dose date + 1)/7;
- Planned treatment duration (weeks) = (number of cycles started x 4) - (number of weeks in the last cycle after permanent treatment discontinuation or data cutoff for those on-treatment);
- Intended treatment duration (weeks) = (last zero/non-zero dose date – first dose date)/7 + 1.

The planned dose of dexamethasone for a given cycle is defined as:

- Cycle 0:  
Planned dose (mg/cycle) = 20 (mg) × 3.
- Cycle 1 & 2:  
Planned dose (mg/cycle) = 20 (mg) × 4.

**Note:** For last cycle, subtract planned doses after a participant permanently discontinues treatment or data cutoff for those on-treatment.

The total planned dose is the sum of the total planned dose across all cycles.

The cumulative dose (mg) of dexamethasone per cycle is the sum of the actual dose levels that the participant received within that cycle (ie, total dose administered [mg]).

The overall planned DI is defined as:

- Overall Planned DI (mg/week) = Total planned dose (mg)/(planned treatment duration in weeks).

The overall DI, RD, and the RDI will be calculated for each participant overall across all cycles as follows:

- Overall DI (mg/week) = Total cumulative dose (mg)/ Intended treatment duration (weeks);
- Overall Planned DI (mg/week) = Total planned dose (mg)/(planned treatment duration in weeks);
- Overall RD (%) = [Total cumulative dose (mg) / Total planned dose (mg)] × 100;
- Overall RDI (%) = [Overall DI (mg/week) / Overall Planned DI (mg/week)] × 100.

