### 5.2.5. Definition of Cycle and Cycle Day

Cycle start and end dates are derived per participant. The definition for each cycle is driven by study intervention PF-06863135.

The first cycle of PF-06863135 is 35 days from Cycle 0 Day 1 through Cycle 1 Day 28 (the 1-week period after the priming dose of PF-06863135 on Cycle 0 Day 1, plus 4 weeks of combination study intervention that begins on Cycle 1 Day 1). Starting from Cycle 2, PF-06863135 is administered on Days 1, 8, 15 and 22 of each 28-day cycle. As described in Section 12.5.2 of the protocol, if a participant has received QW dosing for at least 6 cycles and has achieved an IMWG response category of PR or better persisting for at least 2 months, the dosing interval will be changed from QW to Q2W. If the participant subsequently begins to have an increase of disease burden not yet qualifying as PD according to IMWG criteria, dose intervals should return to weekly dosing. If the dose interval is changed, cycles should remain the same length (ie, 4-week cycles). In either dosing scenario, the nominal cycle length is 28 days (except Cycle 1 is 35 days).

- For Cycle X, the actual cycle start date for each participant is the earliest start date of dosing in the Cycle X Day 1 visit CRF exposure page, if the participant received study intervention on that visit (ie, any study drug with dose >0 at that visit).

- For all but the last cycle:
  - Actual cycle stop date is calculated as the start date of the next cycle minus 1 day;
  - Actual cycle duration is calculated from Day 1 of a cycle to the day prior to Day 1 of the next cycle, as follows:
    - Actual Cycle Duration (weeks) = (cycle stop date – cycle start date + 1)/7.

For the last cycle, actual cycle duration is the planned cycle duration and actual cycle stop date is calculated as actual cycle start date + 28 – 1 day.

The cycle day will be calculated as:

$$\text{Cycle day} = \text{Date of the assessment/event} - \text{cycle start date} + 1.$$

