### **6.6.4. Concomitant Medications and Nondrug Treatments**

The following analyses will be based on the Safety Analysis Set.

**Concomitant medications** are medications, other than study medications, which started prior to first dose date of study intervention and continued on during the on-treatment period as well as those started during the on-treatment period. **Prior medications** are medications, other than study medications, which are started before the first dose of study intervention.

Prior and concomitant medications will be summarized from the ‘Prior and Concomitant Medications’ eCRF page. **Pre-medications** required for CRS will also be summarized separately from the ‘Pre-Medication Treatment’ eCRF page.

Summary of prior medications, concomitant medications and summary of pre-medications will include the number and percentage of participants by Anatomical Therapeutic Chemical (ATC) Classification Level 2 and preferred term. A participant will be counted only once within a given drug class and within a given drug name, even if he or she received the same medication at different times. If any prior or concomitant medication is classified into multiple ATC classes, the medication will be summarized separately under each of these ATC classes. The summary tables will be sorted in descending frequency of ATC class and descending frequency of drug name in a given ATC class in Phase 2. In case of equal frequency regarding ATC class (respectively drug name), alphabetical order will be used. Medications without an ATC classification Level 2 coded term will be summarized under the ‘Unavailable ATC classification’ category.

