A minimum of 2 days should be maintained between the 2 step-up doses (C0D1 and C0D4) and a minimum of 3 days between C0D4 and the first full dose (C0D8); a minimum of 6 days is required between doses thereafter.

The summary of treatment exposure to elranatamab will include the following information:

- Treatment duration (weeks);
- Number of cycles started per participant (mean, median, min, max);
- Number and percent of participants starting a cycle (any cycle, cycle 0, 1, 2, 3, 4, 5, 6, 7, 8, 9, 10, 11, >=12 cycles);
- Total cumulative dose (mg);
- Overall dose intensity (mg/week);
- Overall relative dose (%);
- Overall relative dose intensity (%);
- Number and percent of participants after 6 cycles who switched from QW to Q2W;
- Number and percent of participants, among those switching from QW to Q2W, who switched back to QW.

The treatment duration of elranatamab (in weeks) during the study for a participant is defined as:

- Treatment duration (weeks) = (last dose date – first dose date + 1)/7

Planned treatment duration and intended treatment duration are needed to calculate dose intensity (DI) and relative dose intensity (RDI). It is defined as follows:

- Planned treatment duration (weeks) = 2(2 week for Cycle 0) + number of cycles started × 4 - (number of weeks in the last cycle after permanent treatment discontinuation or data cutoff for those on-treatment).
- Intended treatment duration (weeks) = (last zero/non-zero dose date – first dose date)/7 + 1 if on QW or 2 if on Q2W

**Note:** If C0D4 is the last visit and dose is given at this visit, duration is 1 week.

The planned dose for a given cycle is defined as:

- Cycle 0:
  - Planned dose (mg/cycle) = Planned priming dose(s) per protocol during C0
- After Cycle 0:
  - If the participant is on QW dosing schedule for the cycle:  
Planned dose (mg/cycle) = Full dose × 4
  - If the participant is on Q2W dosing schedule for the cycle:  
Planned dose (mg/cycle) = Full dose × 2

**Note:** Full dose=44 or 76 mg depends on DLs. For the last cycle, subtract planned doses after a participant permanently discontinues treatment or data cutoff for those on-treatment.

The total planned dose is the sum of the total planned dose across all cycles.

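### Sub-study B: dexamethasone planned duration leaves out the two C0 weeks, so with C1 and C2 counted a fully taken course reads an overall RDI of 80%

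*SAP*

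**What the plan says.** All of the following is in the Sub-study B SAP unless stated otherwise.

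- **Schedule (Section 6.6.3.3).** "Dexamethasone 20 mg will be administered three time in C0 (D1, D4, D8", then weekly on days 1, 8, 15 and 22 of C1 and C2.
- **Planned dose (6.6.3.3).** For Cycle 0, "Planned dose (mg/cycle) = 20 (mg) × 3". For each of Cycles 1 and 2 it is 20 mg × 4. No planned dose is defined for any later cycle.
- **Planned duration (6.6.3.3).** "Planned treatment duration (weeks) = (number of cycles started x 4) - (number of weeks in the last cycle after permanent treatment discontinuation", or after data cutoff for participants still on treatment.
- **Intended duration (6.6.3.3).** "Intended treatment duration (weeks) = (last zero/non-zero dose date" minus the first dose date, divided by 7, plus 1.
- **RDI (6.6.3.3).** Overall dose intensity (DI) is cumulative dose over intended weeks. Planned DI is total planned dose over planned weeks. Overall RDI is their ratio and is one of the listed dexamethasone exposure results. Overall relative dose (RD), the ratio of doses alone, is also defined.
- **Elranatamab (6.6.3.1).** Planned duration opens with "2(2 week for Cycle 0) + number of cycles started" × 4, so C0 is added separately from the started cycles.
- **Start of dexamethasone (6.6.3.2 and Table 5).** Section 6.6.3.2 says "Starting on Cycle 1, the first dosing of the two combination partners (lenalidomide and dexamethasone) will be initiated". Table 5 also starts dexamethasone at C1D1.

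**The concern.** Planned DI divides a dose by a duration, and the two should cover the same period. In Section 6.6.3.3 the dose covers C0 to C2, while the duration, on its most natural reading, covers C1 and C2 only. Intended duration, which sits in the other half of the ratio, does include C0. The planned-duration formula is the same as the one for lenalidomide. It suits lenalidomide, which starts at C1 and continues in every cycle. It does not suit a drug scheduled from C0D1 and ending in C2.

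RDI tells the reader whether the planned regimen was delivered. Here a participant who missed nothing would appear under-dosed by a fifth, and a participant who stopped during C0 would give a division by zero.

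A second, smaller gap is that the text does not say that the cycles started are dexamethasone cycles only.

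**Working it through.** The SAP states no dexamethasone RDI, so there is no figure of its own to reproduce. The check applies its formulas directly.

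**Inputs**

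- Doses: 3 in C0, 4 in C1 and 4 in C2, which is 11 doses of 20 mg = 220 mg (Section 6.6.3.3).
- Planned dose: 60 + 80 + 80 = 220 mg (Section 6.6.3.3).
- Length of C0: 14 days (Section 2.2, Dose Escalation Design). Study days are therefore C0D1 = 1, C0D8 = 8, C1D1 = 15, C1D22 = 36 and C2D22 = 64.
- No delays or missed doses, and no weeks subtracted at the end of the last cycle.

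**Formula.** RDI = (cumulative dose / intended weeks) / (planned dose / planned weeks). With full compliance the doses cancel and RDI = planned weeks / intended weeks.

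**Control: elranatamab through C2D22, weekly dosing.** Intended (64 − 1)/7 + 1 = 10 weeks; planned 2 + 2 × 4 = 10 weeks. The two agree, so that formula behaves as it should.

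**Dexamethasone as written, with C1 and C2 as the started cycles**

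| Participant | Dose taken and planned | Intended weeks | Planned weeks | RDI |
|---|---|---|---|---|
| All 11 doses | 220 mg | (64 − 1)/7 + 1 = 10 | 2 × 4 = 8 | (220/10)/(220/8) = 22/27.5 = 80% |
| C0 and C1 only | 140 mg | (36 − 1)/7 + 1 = 6 | 1 × 4 = 4 | 4/6 = 66.7% |
| C0 only | 60 mg | (8 − 1)/7 + 1 = 2 | 0 | undefined |

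**Sensitivity to the meaning of cycles started.** If every study cycle counted and the last was complete, planned weeks would be 4N and RDI would be 4N/10 = 40% × N: 80% at N = 2, 120% at N = 3 and 240% at N = 6. These N values are illustrative.

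**After the proposed change.** All 11 doses: 10/10 = 100%. C0 and C1 only: (2 + 4)/6 = 100%. C0 only: 2/2 = 100%. If the C0 doses are removed as not study drug, intended duration is (64 − 15)/7 + 1 = 8 weeks, planned duration is 8 weeks, and the completed course again reads 100%.

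**Why completion has to be defined.** If the end of the course at C2D22 were treated as permanent discontinuation, 6 days would be subtracted. The corrected formula would then give (10 − 6/7)/10 = 9.14/10 = 91.4%, and the formula as written would give (8 − 6/7)/10 = 71.4%.

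**The case against.** **Scope of the cycle count.** The formula appears under a lead-in about dexamethasone duration, planned dose is defined only for C0 to C2, and the parallel formula in the Sub-study A SAP (Section 6.6.3.2) names nirogacestat discontinuation explicitly. Cycles started is therefore most naturally read as dexamethasone cycles. This stands. Section 5.2.5 of the master SAP says "The definition for each cycle is driven by study intervention PF-06863135", from which a reader might infer that all elranatamab cycles count and that RDI will run to 120%, 240% or more. The documents do not establish that. The master text describes Sub-study A timing, with a 35-day first cycle, and the high values need cycles with no planned dexamethasone to be counted. They justify a clarification and are not the plan's result.

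**C0 might itself be a started cycle.** Section 6.6.3.1 lists cycle 0 among the cycles a participant can start. Counting it as four weeks gives 12 planned weeks and an RDI of 12/10 = 120%. That reading does not rescue the formula, and the separate C0 term for elranatamab argues against it.

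**C0 dexamethasone may be premedication.** Table 5 and Section 6.6.3.2 start the drug at C1, and Section 6.6.4 of the master SAP says that premedication "required for CRS will also be summarized separately from the" premedication page of the eCRF. A reader might infer that the C0 doses will be recorded only there while 60 mg stays in planned dose, which would put RD at 160/220 = 72.7% for full compliance. Nothing in the documents shows that recording. The conflict over when dexamethasone starts is real and needs settling, but Section 6.6.3.3 itself explicitly plans the C0 dose.

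**Low stakes.** RD, which uses no durations, still reads 220/220 = 100%, and an implausible RDI might be caught against it at programming. That limits the harm. It does not make the stated formula right, and an unrecorded programming correction would depart from the SAP.

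**Conclusion.** The formula is wrong as written. Planned dose and intended duration include C0; planned duration does not. With C1 and C2 as the started cycles, no delays, and nothing subtracted at the end of the last cycle, a completed 11-dose course reads 80% instead of 100%, a course fully taken through C0 and C1 reads 66.7%, and a C0-only participant has no defined RDI. The 80% also rests on the first dexamethasone dose falling on C0D1, as Section 6.6.3.3 schedules it.

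The lack of an explicit limit to dexamethasone cycles is a point of clarity, since an RDI above 100% follows only if cycles without planned dexamethasone are counted.

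The effect is confined to a descriptive exposure summary. RD, DLT, safety and efficacy results are not touched by the duration error, and a reader should not infer otherwise.

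**What to change.** In Section 6.6.3.3 of the Sub-study B SAP:

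1. Define dexamethasone planned duration as 2 weeks for C0 plus 4 weeks for each of C1 and C2 started, to a maximum of 10 weeks, less the weeks after early permanent discontinuation of dexamethasone or after data cutoff. This also restricts the count to dexamethasone cycles.
2. State that completing the planned course at C2 is not discontinuation. Without this sentence a completed course may still fall short of 100%.
3. Reconcile the C0 doses with Table 5 and Section 6.6.3.2. If they are not study-drug doses, remove both the 60 mg and the two C0 weeks, for a maximum of 8 weeks.

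A course cut mid-week can still differ from 100%, because intended duration credits a full week after the last dose. At a cutoff on C1D10 (5 doses, 100 mg, intended (22 − 1)/7 + 1 = 4 weeks) the RDI is (4 − 18/7)/4 = 35.7% as written and (6 − 18/7)/4 = 85.7% after the change.

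The cost is SAP wording and programming only.
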